#### Adverse events:

All AE/SAE will be assessed and documented by the investigator according to the categories detailed below.

- Seriousness (yes/no):
  - Patients with SAE at any time in the course of the study will be counted in the category SAE. All patients with AE but not serious at any time will be counted in the category AE.
- Intensity (mild, moderate, severe)
- Causal relationship (yes/no)
- Action taken with study treatment (drug withdrawn, drug interrupted, dose reduced, dose not changed, dose increased, not applicable, unknown)
- Other specific treatments (none, remedial drug therapy, other)
- Outcome (recovered/resolved, recovered/resolved with sequelae, not recovered/not resolved, life-threatening, fatal, unknown)

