## 9.2 Statistical methods

Descriptive or summary statistics will be displayed for continuous data and for categorical data. All continuous variables will be summarised using the following statistics: n (non-missing sample size), mean, 95 % confidence interval, standard deviation, median, maximum and minimum. The frequency and percentages (based on the non-missing sample size) of observed levels will be reported for all categorical measures. In general, all data will be listed, sorted by subject and visit number. All summary tables will be annotated with the total population size relevant to that table/treatment, including any missing observations.

Comparisons will be tested at the 2-sided 5% significance level. For the primary study endpoint, a one-sided significance level of 5% will be assumed.

T-tests for independent samples will be used for single comparisons between treatment arms (like the primary study endpoint). Analyses of the continuous variables over time will be performed as paired t-Test, repeated measures analysis of variance or mixed models. All analyses of categorical measures will be performed using Fisher's exact test, McNemar's Test or  $\chi^2$  test. Previous correlation analyses of outcome variables and possible predictors will provide evidence for inclusion in analysis. In this trial, most relevant time points for analyses of longitudinal data for secondary study endpoints are at baseline (V1) and after end of treatment (V6).

Individual listings of treatment-emergent adverse events will be provided. The incidence of treatment-emergent adverse events, respectively, will be summarized using WHO SOC terms. Analysis of adverse events will be based on the safety analysis set.

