### 10.1.3 Serious adverse events and serious adverse reactions

A serious adverse event (SAE) or serious adverse drug reaction (SADR) is classified as any untoward medical occurrence that, at any dose, meets any of the following criteria (a - f):

- results in death
- is life-threatening

The term 'life-threatening' in the definition refers to an event in which the patient was at risk of death at the time of the event, it does not refer to an event which hypothetically might have caused death if it were more severe.

requires inpatient hospitalization or prolongation of existing hospitalization

A hospitalization or prolongation of hospitalization will not be regarded as an SAE if at least one of the following exceptions is met:

- the admission results in a hospital stay of less than 12 hours
- the admission is pre-planned(i.e. elective or scheduled surgery arranged prior to the start of the study that is written in the patient / study file)
- the admission is not associated with an AE (e.g. social hospitalization for purposes of respite care)

However, it should be noted that invasive treatment during any hospitalization may fulfill the criterion of 'medically important' and as such may be reportable as an SAE dependent on clinical judgment. In addition, where local regulatory authorities specifically require a more stringent definition, the local regulation takes precedence.

- results in persistent or significant disability / incapacity
   Disability means a substantial disruption of a person's ability to conduct normal life's functions.
- is a congenital anomaly / birth defect
- is another medically important serious event as judged by the investigator

If an AE is classified as an SAE, this is documented on a separate SAE sheet in addition to the standard AE documentation.

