#### **6.12.3** Adverse Events

Individual listings of treatment-emergent adverse events will be generated. The incidence of treatment-emergent adverse events, respectively, will be summarized using WHO SOC terms. Analysis of adverse events will be based on the SAF.

Listings of AEs, SAEs, ADRs and SADRs will be generated. The following variables will be included in the listing:

- Patient ID
- Treatment group
- Age/gender/race
- Verbatim Term
- AE start date and end date/ongoing
- AE Duration
- Study day onset
- Intensity
- Relationship of AE to study drug: unrelated or related
- Action taken
- Treatment
- Outcome

Listing of SADRs resulting in death and study discontinuation will also be generated.

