#### 6.12.4 Bleedings

The results for major, CRNM, minor and total bleeding will be documented. Total bleeding includes any bleeding event (including CRNM, minor and major bleeding). These analyses will be performed on SAF and PPS.

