#### 7.8.3 Adverse Events

				Comparison of					
Adverse Events			Total		Rivaroxaban		spirin	Proportions	
		N	%	N	%	Ν	%	p-Value	
Number of	AE								
	SAE								
Patients	ADR								
	SADR								
	AE							-	
Number of Events	SAE								
	ADR								
	SADR								

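### If the SAP 4.7.3 counting rule is carried into table 7.8.3, the patient row labelled AE means non-serious AEs only, and no any-AE count is shown or tested

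*SAP*

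**What the plan says.** Under the variable Seriousness, SAP 4.7.3 sets two rules for counting patients. First: "Patients with SAE at any time in the course of the study will be counted in the category SAE". Second: "All patients with AE but not serious at any time will be counted in the category AE".

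Mock table 7.8.3 has patient rows for AE, SAE, ADR and SADR, followed by event rows, with a p-value column comparing proportions between arms. It has no row for any AE. SAP 6.3 assigns Fisher's exact test to two-category variables, by default two-sided at 5%.

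Three other places bear on the reading:

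- Protocol 10.1.3 treats a serious event as an AE that receives extra paperwork: "If an AE is classified as an SAE, this is documented on a separate SAE sheet in addition to the standard AE documentation".
- SAP 4.7.3 also sorts bleeding patients by their worst category, but SAP 6.12.4 adds an inclusive count ("Total bleeding includes any bleeding event (including CRNM, minor and major bleeding"), and mock table 7.8.4 has a row for it.
- SAP 6.12.3 plans a separate summary: "The incidence of treatment-emergent adverse events, respectively, will be summarized using WHO SOC terms". It also provides individual listings. Protocol 9.2 plans the same summary.

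**The concern.** By convention, and by the protocol's own definition, a row headed AE holds every patient with at least one adverse event, and SAE is a subset of it. Under the SAP rule, a patient with a serious event leaves the AE row even if that patient also had non-serious events. The label does not say so, and the row carries a p-value.

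At stake is how the overall AE comparison reads. A drug that turns some patients' non-serious experience into a serious one would show fewer patients with AE and could gain a favourable p-value on that row. This is an open-label comparison in which Protocol 2.5 calls bleeding the major risk of anticoagulation and says that no direct bleeding comparison of the two regimens exists. A general AE row that can move the wrong way is unhelpful there.

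**Working it through.** **Inputs.** The counting rule is from SAP 4.7.3, the rows from SAP 7.8.3 and the test from SAP 6.3. The denominator of 94 per arm is the planned size in SAP 2.4 (141 / 0.75 = 188; 188 / 2 = 94). The documents give no AE or SAE rates, so all event counts below are assumptions. There is no stated AE figure to reproduce.

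**Formula.** In each arm let A be the patients with any AE, serious or not, and S the patients with any SAE. Under the rule:

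- AE row = A − S
- difference between arms in the AE row = (difference in A) − (difference in S)

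The arm with more SAEs therefore shows the lower AE row whenever its excess in S is larger than its excess in A. If an additional SAE occurs in a patient with no other AE, A and S both rise by one and the AE row does not move.

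**Two worked cases** (two-sided Fisher's exact test, first arm v second arm):

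1. Any AE 60 v 60 (63.8% each, p = 1.000); SAE 20 v 5 (p = 0.002). AE row: 60 − 20 = 40 (42.6%) v 60 − 5 = 55 (58.5%), p = 0.041, in favour of the arm with four times the SAEs.
2. Any AE 56 v 52 (p = 0.66); SAE 20 v 6 (p = 0.005). AE row: 56 − 20 = 36 (38%) v 52 − 6 = 46 (49%), p = 0.19. A difference of about +4 percentage points in any AE prints as about −11, but that row is not significant.

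**Range over the assumptions:**

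| Any AE | p | SAE | p | AE row under the rule | p |
|---|---|---|---|---|---|
| 60 v 60 | 1.000 | 5 v 5 | 1.000 | 55 v 55 | 1.000 |
| 60 v 60 | 1.000 | 10 v 5 | 0.282 | 50 v 55 | 0.557 |
| 60 v 60 | 1.000 | 15 v 5 | 0.031 | 45 v 55 | 0.188 |
| 60 v 60 | 1.000 | 20 v 5 | 0.002 | 40 v 55 | 0.041 |
| 60 v 60 | 1.000 | 25 v 5 | <0.001 | 35 v 55 | 0.005 |
| 40 v 40 | 1.000 | 20 v 5 | 0.002 | 20 v 35 | 0.024 |
| 50 v 50 | 1.000 | 20 v 5 | 0.002 | 30 v 45 | 0.037 |
| 70 v 70 | 1.000 | 20 v 5 | 0.002 | 50 v 65 | 0.036 |
| 70 v 60 | 0.155 | 20 v 5 | 0.002 | 50 v 55 | 0.557 |
| 75 v 60 | 0.023 | 20 v 5 | 0.002 | 55 v 55 | 1.000 |
| 80 v 60 | 0.001 | 20 v 5 | 0.002 | 60 v 55 | 0.550 |

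The reversal needs a clear SAE imbalance. It ends when the any-AE excess equals the SAE excess (75 v 60: 15 against 15). Even there the row is uninformative: a difference in any AE with p = 0.023 prints as 55 v 55.

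**The case against.** The strongest defence is that nothing is lost. Because the categories are exclusive, the printed AE and SAE patient rows add up to any AE. The SAE row, with its own test, stands beside the AE row and is unaffected by the rule. In every example where the AE row misleads at the 5% level, the SAE row shows the imbalance at p = 0.002 or below. This stands. It limits the fault to a wrong label and a missing tested total. It does not excuse a p-value on a row that means something other than its heading, since the table neither tells the reader to add the rows nor tests the sum.

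A second defence is that the link is inferred. The rule sits under the Seriousness variable, and table 7.8.3 does not refer back to it. The rule is worded for patients, so it does not clearly govern the event rows, and nothing says whether ADR and SADR follow it. This also stands. The application to the AE and SAE patient rows is the likely reading, because the SAP gives no other definition for them, but it is not stated.

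Three stronger inferences are tempting, and the documents do not support them:

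- *That the AE count always falls as serious harm rises.* It falls only when the any-AE total is held fixed.
- *That the plan breaks a promise to report AE incidence.* The incidence planned in Protocol 9.2 and SAP 6.12.3 is by system organ class. It is a separate summary, it does not promise an any-AE patient total, and SAP 4.7.3 does not clearly restrict it to non-serious events.
- *That the main safety result is distorted.* The safety variables named in Protocol 6.1.3 are major and clinically relevant non-major bleeding, and the bleeding table has its inclusive total.

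**Conclusion.** The concern holds in a limited form. If the rule in SAP 4.7.3 is applied to table 7.8.3, the row labelled AE is patients with non-serious AEs only. The any-AE count is then neither shown nor tested. This departs from the protocol's treatment of an SAE as an AE and from the SAP's own handling of bleeding.

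The size depends on rates that the documents do not give. With SAE 20 v 5 among 94 per arm and equal any-AE totals of 40 to 70, the AE row differs by 15 patients in favour of the arm with more SAEs (p = 0.024 to 0.041). With SAE 10 v 5 or 15 v 5 at any AE 60 v 60, it leans the same way without significance (p = 0.557 and 0.188).

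A reader might infer that serious harm would be concealed. It would not be: the SAE row, the listings and the bleeding analysis are untouched, as are the efficacy analyses. This should be fixed, but it does not endanger the trial's main conclusions.

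**What to change.** Either of two changes is enough.

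1. In SAP 4.7.3, define an AE patient as one with at least one treatment-emergent AE, serious or not, with SAE as a subset. Apply the same rule to ADR and SADR. Label the patient rows of table 7.8.3 *any AE*, *any SAE*, *any ADR* and *any SADR*.
2. Keep the exclusive count but relabel it *non-serious AE only*, show it descriptively without a p-value, and add a tested *any AE* row, following the total row already planned for bleeding. State which rule governs ADR and SADR.

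In both cases, add a line in table 7.8.3 that refers to the definition and says whether it also governs the event rows. The cost is a few sentences of SAP wording and one table definition. No new data are needed.

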#### 4.8 Definition of derived variables

#### 4.8.1 Primary variable

#### ΔFBF:

 $\Delta$ FBF (ml/100ml) will be composed of 5 IR baseline measurements and 8 measurements of post-ischemic blood flow. Repeated measurements for IR baseline per visit will be summarized by arithmetic mean.

Changes in FBF (ml/100ml) will be calculated as IR post-ischemic – IR baseline (mean).

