#### 5 Efficacy Endpoints

#### 5.1 Primary endpoint

Comparison of treatment groups for ΔFBF at week 20

Additional primary variable for extension period:

Comparison of treatment groups for pulse wave velocity at week 52

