#### 5.2 Secondary endpoints

- Comparisons of groups and changes from baseline per treatment group for the following variables:
  - o PWV at week 52
  - o Maximal difference between baseline and post-ischemic skin blood flow FBF
  - Change of area under the FBF curve over 10 cycles of venous congestion (compared to baseline/day 0) at week 20 and EoT extension
  - Index of augmentation at weeks 20 and 52
  - o pulse wave velocity at 20 weeks and EoT Extension compared to baseline
  - change of maximal postischemic forearm blood flow during reactive hyperaemia after 5 min of forearm ischemia (FBF max. ml/100ml) at EOT after 52 weeks (EOT Extension)
  - o laboratory parameters (see above) at weeks 20 and 52

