#### 6.3 Hypothesis Testing

Unless otherwise specified all hypotheses will be tested at a 5% level of significance against two-sided alternative hypotheses.

Continuous variables will be analyzed by the following test procedures:

First of all the assumption of normally distributed data will be checked with Shapiro-Wilk test by treatment group. If the hypothesis of normally distributed data cannot be rejected for both treatment groups treatments will be compared by an ANCOVA procedure which includes "treatment" as the main factor and "baseline value" as covariate. T-Tests for independent samples will be used to compare groups at baseline.

In the event that the normality assumption is not warranted, data will be log-transformed and normality assumption of the transformed data will be checked by Shapiro-Wilk test. In case of non-rejection of the hypothesis of normally distributed data for both treatment groups, ANCOVA procedure and t-tests as described above will be performed on the basis of log-transformed data.

Point estimates and 95% CI of the difference in (adjusted) mean change from baseline will be provided if data are evaluated on basis of an ANCOVA procedure.

Otherwise Mann-Whitney's-U test on the basis of original data will be applied for comparison of groups at baseline. Mann-Whitney's-U test on the basis of intra-individual differences to baseline will be applied for treatment comparison per visits after baseline. Wilcoxon's signed rank test will be applied to evaluate changes from baseline per treatment group.

Categorical variables with 2 categories will be analyzed using Fisher's exact test (with Yates correction) to compare proportions between treatment groups. Variables with more than 2 categories will be compared by Pearson's Chi-square test. Additionally for each category, the proportions of treatment groups are compared using an (asymptotic) z test. Significant differences in proportions will be flagged, p-values for the z-test will not be shown.

Missing values will not be imputed.

If necessary, modifications of this general procedure will be described in the following sections of chapter 6.

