#### 6.11.1 Analysis of Primary Endpoint

Primary study endpoint:

The hypothesis H0 is tested against the **one-sided** alternative hypothesis H1

```
H0: \mu_{\Delta FBF,Riva, week 20} \leq \mu_{\Delta FBF, ASS, week 20} vs. H1: \mu_{\Delta FBF, Riva, week 20} > \mu_{\Delta FBF, ASS, week 20}
```

by test procedures for continuous data. In case of non-rejection of the normality hypothesis an ANCOVA procedure for repeated measurements will be applied. For repeated measurements per subject an AR(1)-covariance-structure will be specified. Otherwise ANCOVA for repeated measurements will be based on (Blom-transformed) rank data.

Primary endpoint for the extension period:

The hypotheses

```
H0: \mu_{PWV, Riva, week 52} = \mu_{PWV, ASS, week 52} VS. H1: \mu_{PWV, Riva, week 52} \neq \mu_{PWV, ASS, week 52}
```

will be tested by procedure for continuous data.

Age, gender and duration of diabetes might represent confounding factors and could thus be included as covariates in the statistical model. Models incorporating different combinations of covariates are compared with respect to their model fit. The best fitting model according to the QIC (Quasi-Likelihood information) -criterion will be finally chosen for analysis.

Correction procedures for multiple comparisons are not necessary due to the fact that both primary endpoints consist in single comparisons addressing different variables.

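### The SAP's primary variable (eight post-ischaemic readings minus resting flow, no maximum taken) is not the protocol's change in maximal post-ischaemic forearm blood flow, which is the only FBF variable the 90% power covers

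*SAP*

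**What the plan says.** **Protocol.** The synopsis (study end points), 6.1.1 and 9.1.3 all define the primary variable as the week-20 change in the maximum flow reached after five minutes of forearm ischaemia. The synopsis paragraph on statistical methods also takes the maximum FBF at week 20 as the primary parameter, adjusted for baseline FBF by ANCOVA. Sections 9.1.8 and 9.2 name an independent-samples t-test instead.

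**Sample size.** Protocol 9.1.8 and SAP 2.4 both attach the difference of 1.2 and the SD of 2.4 ml/100ml to changes in maximal FBF, and both label that quantity ΔFBF.

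**SAP definition.** Section 4.8.1 says that ΔFBF "will be composed of 5 IR baseline measurements and 8 measurements of post-ischemic blood flow". The resting readings are averaged, and the variable is post-ischaemic flow minus that mean. No rule reduces the eight post-ischaemic readings to one value.

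**SAP endpoint and model.** Section 5.1 gives the primary endpoint as "Comparison of treatment groups for ΔFBF at week 20". Section 6.11.1 tests it one-sided with a repeated-measures ANCOVA: "For repeated measurements per subject an AR(1)-covariance-structure will be specified".

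**Where the SAP mentions a maximum.** In the endpoint lists, the protocol's variable is clearly named only as a week-52 secondary: "change of maximal postischemic forearm blood flow during reactive hyperaemia after 5 min of forearm ischemia (FBF max. ml/100ml) at EOT after 52 weeks". Another secondary item reads "Maximal difference between baseline and post-ischemic skin blood flow FBF"; it has no time point and mixes skin flow with FBF. The mock tables in 7.6.1 list ΔFBF as eight rows, one per post-ischaemic reading. They show maximal post-ischaemic flow separately, with rows at day 0, week 20 and week 52.

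**The concern.** One symbol carries two meanings within the SAP: change in the maximum in section 2.4, and increment over resting flow across eight readings in 4.8.1, 5.1 and 6.11.1. Followed as written, the plan would test as primary a variable that neither the protocol's endpoint definition nor the SAP's own sample size describes.

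The contrast is also open. Section 6.11.1 writes one mean per arm, which suggests a treatment effect pooled over readings. The mock table gives each of the eight readings its own between-arm effect, p-value and confidence interval at week 20. The text does not even say whether the repeated measurements are readings within a visit or visits. Section 6.11.1 waives multiplicity correction because each primary endpoint is a single comparison, yet for ΔFBF no single comparison is specified. The trial is open-label (protocol 5.10), so a choice left until the data are in hand is hard to defend.

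The number of readings differs too. The SAP's definition uses eight, while protocol 6.2.1 describes ten congestion cycles and SAP 5.2 has "Change of area under the FBF curve over 10 cycles of venous congestion".

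**Working it through.** **1. The plan's own figure, for the maximum.** Inputs from protocol 9.1.8 and SAP 2.4: difference 1.2, SD 2.4, one-sided α = 0.05, power 0.90, dropout 25%.

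- Standardised difference: d = 1.2/2.4 = 0.5.
- Normal approximation: n per arm = 2(1.645 + 1.282)²/0.5² ≈ 68.5, so 69.
- Exact one-sided t-test: 69.2, so 70 per arm.
- Dropout: 70/0.75 = 93.3, so 94 per arm and 188 in total; 188 × 0.75 = 141 evaluable.
- Power from the noncentral t: 0.903 at 70 and 70; 0.905 at 70 and 71.

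The stated 188 and 141 reproduce. The arithmetic is sound for the maximum.

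**2. The definitions side by side.**

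| Place | Variable | Maximum taken? |
|---|---|---|
| Protocol synopsis, 6.1.1, 9.1.3 | Week-20 change in post-ischaemic FBF | Yes |
| Protocol 9.1.8 and SAP 2.4, effect-size assumption | Change in FBF | Yes |
| SAP 4.8.1, 5.1, 6.11.1 | Post-ischaemic minus mean resting flow, eight readings | No |
| SAP 7.6.1, ΔFBF rows | Readings 1 to 8, each minus resting flow | No |
| SAP 7.6.1, separate block | Post-ischaemic flow at day 0, weeks 20 and 52 | Yes, but not as ΔFBF |

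The last two rows rule out reading ΔFBF as an implied maximum: the SAP tabulates the two as different variables.

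**3. What the eight-reading contrast would need.** The documents give no difference, SD or between-reading correlation for it, so its power cannot be derived. The required standardised difference can be. For an unadjusted one-sided t-test at 70 per arm, the noncentrality is d√(70/2) with 138 degrees of freedom. Solving for power 0.90 gives d = 0.497; solving for 0.80 gives d = 0.422. Over an assumed range:

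| d (0.5 is the planned value for the maximum; the others are assumed) | Power at 70 per arm |
|---|---|
| 0.3 | 0.55 |
| 0.4 | 0.76 |
| 0.5 | 0.90 |
| 0.6 | 0.97 |

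**4. Why the direction is open.** Suppose the contrast is the mean of the eight readings, each with SD 2.4 and AR(1) correlation ρ. None of this is in the documents. The variance of the mean is 2.4² × (1/64)ΣΣρ^|i−j|. With 141 evaluable patients and the normal approximation:

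| ρ | SD of the mean | Power, average effect 1.2 | Power, average effect 0.6 |
|---|---|---|---|
| 0.5 | 1.34 | 1.00 | 0.84 |
| 0.7 | 1.66 | 1.00 | 0.69 |
| 0.9 | 2.11 | 0.96 | 0.52 |

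Averaging reduces noise, but if the treatment effect is concentrated near the peak it also dilutes the effect. Which of the two dominates cannot be judged from the documents.

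**The case against.** **The protocol is not uniform.** Its primary objective (2.2) and the opening line of 9.1.8 speak only of change in flow after ischaemia, and the objective could be read as subtracting resting flow. This stands as far as subtraction goes. It does not reach the maximum, which every endpoint definition and the effect-size assumption name.

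**SAP 4.8.1 may be incomplete rather than different.** Read alone, that is possible, since 2.4 ties the same symbol to the maximum. The eight ΔFBF rows, the separate rows for the maximum and the AR(1) structure make it unlikely. Even on this reading the primary variable is undefined.

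**The week-20 maximum would still be reported.** True: the mock tables give its change from day 0 with between-arm effect, p-value and confidence interval. The change from day 0 is not lost for ΔFBF either, because SAP 6.3 uses the baseline value as covariate. What is lost is the designation of the maximum as primary.

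**The break-even ignores covariate adjustment.** Correct. If the day-0 value correlates r with the week-20 value, the requirement falls to about 0.497√(1 − r²). For assumed r of 0.3, 0.5 and 0.7 this is 0.47, 0.43 and 0.36. No loss of power is shown, only that 90% is not established.

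**The protocol calls the trial exploratory and a pilot** (section 1, 2.1, 9.1.5). That lowers the stakes, but the trial still has a designated, powered primary endpoint with a one-sided test, and its variable should be the protocol's.

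**Conclusion.** The concern holds and should be fixed before the primary analysis is run. As written, the SAP tests a primary variable other than the protocol's, through a contrast it does not name. The 188 patients and 90% power are correct for the change in maximal FBF (0.903 to 0.905) and are not established for the eight-reading variable. The calculated power rests on the plan's own 1.2 and 2.4, a one-sided 5% t-test and 70 to 71 evaluable patients per arm. Every power figure for the eight-reading contrast rests on assumed inputs and shows only that power could fall on either side of 90%.

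**What to change.** - In SAP 4.8.1, 5.1 and 6.11.1, define the primary variable as maximal post-ischaemic FBF at week 20, one value per patient. Compare arms by ANCOVA with day-0 maximal FBF as covariate, one-sided 5%. This follows the protocol synopsis and SAP 6.3; record it as a choice, since protocol 9.1.8 and 9.2 name a t-test.
- State whether resting flow is subtracted before the maximum is taken.
- State which parts of the 6.3 and 6.11.1 procedure (normality check, rank transformation, covariate selection) still apply to a single-value primary.
- Give the eight-reading increment its own symbol and supportive status, with one named contrast.
- Reconcile eight readings in SAP 4.8.1 with ten cycles in protocol 6.2.1 and SAP 5.2.
- If the sponsor prefers the eight-reading variable as primary, name one contrast, justify the departure from the protocol, and give that contrast its own effect size, SD and power.

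The cost is SAP wording only. The maximum comes from readings already taken and has day-0 and week-20 rows in the mock tables. Because treatment is open-label and SAP section 1 ties revisions to blinded review, date the change and record that it was made without sight of results by arm.
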